10.3.6. Brief Pain Inventory (BPI) Short Form

Changes from baseline for pain severity and pain interference will be analysed using a MMRM. The model will include fixed terms for treatment, visit and the treatment-by-visit interaction. The model will also include the stratification mutation factor, continuous baseline score and continuous baseline distance walked during the 12MWT as covariates. An unstructured covariance structure will be used, and the model will allow the covariance matrix to differ between treatment groups. If the analysis fails to converge, then a Toeplitz structure will be used. The Kenward-Rogers approximation will be used to estimate the denominator degrees of freedom. The treatment comparison for the change from baseline at each visit will be estimated. The estimates, standard errors, 95% confidence intervals and associated p-values will be presented for each visit.

Observed and change from baseline values will be summarized at each visit both including and excluding predicted values using descriptive statistics for the pain severity and pain interference scores. Predicted values for a subject will be the predicted values from the MMRM analysis. The associated 95% confidence intervals for the observed and change from baseline means will also be presented.

Mean plots of observed and change from baseline values, with 95% confidence intervals, will be presented by treatment group with visit on the x-axis. A reference line for no change (i.e., $y=0$) will be included in the change from baseline plot.

Categorical shift tables of change from baseline for pain severity and pain interference showing improvement (at least a 1.5-point decrease in score), no change (less than a 1.5-point change in either direction) or worsening (at least a 1.5-point increase in score) at each visit will be summarized. The table will include categories for withdrawn and missing. Percentages will not be presented for the withdrawn and missing rows, and the percentages presented will use the number of non-missing values as the denominator. In addition, to account for subjects at the extreme ends of the scale, the shift table will also include the percent improving or worsening based on those subjects who have the potential to improve or worsen respectively.

The summary and MMRM analysis may be repeated excluding subjects who have a baseline pain severity score <4.

Pain severity and pain interference scores and changes from baseline will be listed with the raw data.

10.3.7. Work Productivity and Activity Impairment Questionnaire: Specific Health Problems (WPAI: SHP)

Changes from baseline for WPAI scores, except percent activity impairment, will be analysed using a MMRM for subjects who were employed at baseline. The model will include fixed terms for treatment, visit and the treatment-by-visit interaction. The model will also include the stratification mutation factor, continuous baseline score and continuous baseline distance walked during the 12MWT as covariates. An unstructured covariance structure will be used, and the model will allow the covariance matrix to differ between treatment groups. If the analysis fails to converge, then a Toeplitz structure will be used. The Kenward-Rogers approximation will be used to estimate the denominator degrees of freedom. The treatment comparison for the change from baseline at each visit will be estimated. The estimates, standard errors, 95% confidence intervals and associated p-values will be presented for each visit. The analysis will be repeated for percent of activity impairment which will be based on all subjects.

WPAI scores, except percent activity impairment, will only be summarized for those subjects who are employed. Observed and change from baseline values will be summarized by visit both including and excluding predicted values using descriptive statistics for the 4 WPAI scores. Predicted values for a subject will be the predicted values from the MMRM analysis. The associated 95% confidence intervals for the observed and change from baseline means will also be presented.

Mean plots of observed and change from baseline values, with 95% confidence intervals, will be presented by treatment group with visit on the x-axis. A reference line for no change (i.e., $y=0$) will be included in the change from baseline plot.

WPAI score values will be presented to 0 decimal places.

10.3.8. Patient Global Impression of Change (PGIC) – Muscle Symptoms and Fatigue Symptoms

PGIC is only assessed at the end of study treatment (Week 24 or early termination). Data will be included regardless of the duration between the subject's last dose of study medication and the assessment.

Subjects with no PGIC assessment will be considered as missing unless the incidence of missing PGIC data exceeds 5%. If more than 5% of subjects do not complete the PGIC at

Week 24 or the early termination visit, multiple imputation, using ordinal logistic regression (refer to Section 8.3.1) will be adopted to account for their missing data. Subjects who die prior to their PGIC assessment will be imputed as ‘very much worse’.

Both PGIC numeric scores will be analysed using ANCOVA. The model will include a fixed term for treatment and the mutation stratification factor and continuous baseline distance walked during the 12MWT as covariates. The treatment comparison will be estimated, along with its standard error, 95% confidence interval and associated p-value.

A supplementary analysis will also be performed using a while on treatment strategy. In this analysis only assessments within 7 days of the last dose of study treatment will be included. The numeric score will be analysed using ANCOVA using the same model as stated above.

A logistic regression analysis will be performed on the responder exploratory endpoints. Subjects who early terminate with no PGIC assessment will be assumed to be a non-responder. The model will include a fixed term for treatment and the mutation stratification factor and continuous baseline distance walked during the 12MWT as covariates. The estimated odds ratios, 95% confidence intervals and associated p-value for the odds ratios will be presented, together with the exponentiated least squares means treatment estimates and standard errors.

In addition, both PGIC scores will be summarized as a categorical variable for the FAS. The table will include categories for withdrawn (if the subject withdraws prior to the Week 24 visit and does not complete the PGIC at an Early Termination visit) and missing. Percentages will not be presented for the withdrawn and missing rows, and the percentages presented will use the number of non-missing values as the denominator.

10.3.9. 6-Minute Walk Distances (Derived from 12MWD)

The first and last 6-minute walk distances derived from the 12MWD will be analysed in the same way as the primary analysis. The model will include fixed terms for treatment, visit and the treatment-by-visit interaction. The model will also include the stratification mutation factor and continuous baseline distance walked during the 12MWT as covariates. The baseline 6-minute walk distance will not be included in the model as a covariate as this will be correlated with the baseline 12MWD already included in the model. Note that if a subject’s 12MWD is incomplete but they walk for longer than 6 minutes then only the last 6-minute period will be classified as incomplete and imputation rules applied. For example if a subject walks for 10 minutes and the walk is adjudicated as ‘ambulatory subject unwilling to, or prevented from, performing the test for reasons possibly related to PMM or study treatment’ then the worst case imputation will only apply to the last 6 minutes.

In addition to the summary presentation, mean plots for observed, change from baseline and percent change from baseline values, with 95% confidence intervals, will be presented by treatment group and 6-minute time period with visit on the x-axis. A reference line for no change (i.e., $y=0$) will be included in the change from baseline and percent change from baseline plots.

The first and last 6-minute walk distance values, mean, median, minimum and maximum will all be presented to 2 decimal places and SD will be presented to 3 decimal places.

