4.3. PATIENT GLOBAL IMPRESSION OF CHANGE (PGIC) – MUSCLE SYMPTOMS AND FATIGUE SYMPTOMS

The subject is asked to rate both their change in PMM muscle symptoms and change in PMM fatigue symptoms at Week 24 (or, if applicable, the Early Termination visit). The PGIC has a 7-point scale from 'Very Much Improved' to 'Very Much Worse'. This will be converted to a numeric scale from 3 (very much improved) to -3 (very much worse); hence a value of 0 will mean no change. These scores are exploratory endpoints.

Additionally, responder endpoints for both muscle symptoms and fatigue symptoms will be analysed, which is defined as a response of ‘Very Much Improved’ or ‘Moderately Improved’. The PGIC responder endpoints are also exploratory endpoints.

4.4. 30 SECOND SIT TO STAND TEST (30STS)

The purpose of the 30 second sit-to-stand test (30STS) exploratory endpoint is to assess leg strength and endurance. Subjects are required to sit and rise to a full standing position as many times as they can in 30 seconds. A subject should only conduct the test if they are able to stand without using their arms to assist them out of the chair. A score of zero and a reason for not completing the test will be noted in the electronic Case Report Form (eCRF) in these circumstances.

Subjects will perform the test at Baseline, Week 12 and Week 24 visits. If applicable, the test will also be performed at the Early Termination visit.

For each visit changes from baseline will be calculated.

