of 4 days of data will be required for each visit. If there are 3 days or fewer of diary data for a visit, then the step count endpoints will be excluded from the analyses and identified in the data listing. The baseline will be calculated over the last 7 consecutive days of recordings prior to Day 1. If there are no 7 consecutive day periods with recordings, then the latest 7-day period with the most amount of completed days in the baseline period will be used. For post baseline visits (except Week 4) all diary data collected in the analysis visit window will be considered (refer to [Section 8.4](#)) and the 7 consecutive days finishing closest to the target visit date will be used. For Week 4 the lower limit of the analysis window will be widened to allow for the fact that the diary opens 2 weeks prior to the target visit date. If there are no 7 consecutive day periods with recordings, then the 7-day period with the most amount of completed days will be used.

For each visit changes from baseline and percent changes from baseline will be calculated.

4.6. PATIENT GLOBAL IMPRESSION OF SEVERITY (PGIS) SCORE - MUSCLE SYMPTOMS AND FATIGUE SYMPTOMS

At Screening, Baseline, Week 4, Week 12, Week 18 and Week 24 visits, the subject will be asked to rate the severity of their PMM for muscle symptoms and for PMM fatigue symptoms over the past 7 days. If applicable, they will be asked the questions at the Early Termination visit. Both the PGIS muscle symptoms and PGIS fatigue symptoms are exploratory endpoints.

The scale has 5 levels from ‘Absent’ to ‘Very Severe’.

For each visit changes from baseline will be calculated for the two symptom scores.

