Missing values will be imputed using the technique of multiple imputations. Ordinal regression will be used to impute the monotone missing data. Week 12 and Week 24 data will then be analysed separately using ordinal logistic regression analysis for each symptom. The model will include a fixed term for treatment. The model will also include the stratification mutation factor, baseline score and baseline distance walked during the 12MWT as covariates. If there are few counts in one or more of the response categories causing issues with model convergence then categories will be combined in a logical way (e.g., only adjacent categories will be combined) to reduce the number of categories. The proportional odds assumption will be checked using the Score test; if the assumption does not hold then a partial or non-proportional model will be considered. The estimated odds ratios, p-values and 2-sided 95% confidence intervals for the odds ratios will be presented.

Categorical shift tables from baseline at each visit will be summarized including marginal totals. The table will include categories for withdrawn and missing. Percentages will not be presented for the withdrawn and missing rows, and the percentages presented will use the number of non-missing values as the denominator. In addition, to account for subjects at the extreme ends of the scale, the shift table will be repeated for improvement, no change or worsening from baseline at each visit, based on those subjects who have the potential to improve or worsen, respectively.

Stacked bar charts will be presented for the proportion of subjects at each of the PGIS scores by visit for each of the treatment groups. The categories will include each of the PGIS levels and missing and withdrawn.

10.3.4. 36 Item Short Form Survey (SF-36)

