  class treatment mutation(ref='Other');  
  model pgic=mutation base12mwd treatment / ddfm=kr solution;  
  lsmeans treatment / cl diff;  
  estimate 'REN001 - Placebo' treatment 1 -1/cl;  
run;
```

Assumptions:

- treatment is 2 levels e.g. 1=REN001; 2=Placebo
- mutation is 2 levels e.g. 1=m.3243>G; 2=Other
- pgic is the numeric score
- base12mwd is the Baseline 12MWD

7: PGIC – Logistic regression.

```
proc logistic data=<dataset>;  
  class treatment mutation/param=glm;  
  model pgic=mutation base12mwd treatment/expb;  
  lsmeans treatment / cl exp diff;  
  estimate 'REN001 - Placebo' treatment 1 -1/exp cl;  
run;
```

Assumptions:

- treatment is 2 levels e.g. 1=REN001; 2=Placebo
- mutation is 2 levels e.g. 1=m.3243>G; 2=Other
- pgic is 2 levels responder endpoint e.g. 1=yes; 2=no
- base12mwd is the Baseline 12MWD

8: PGIC – monotone multiple imputation.

```
proc mi data=<dataset> seed=<seednumber> out==<outmidataset1> nimpute=25;  
  by treatment;  
  class pgic mutation;  
  monotone logistic(pgic=mutation base12mwd / details);  
  var mutation base12mwd pgic;  
run;
```

Assumptions:

- Dataset has one record per subject in a horizontal structure
- pgic is the numeric ordinal score (range of -3 to 3)
- mutation is 2 levels e.g. 1=m.3243>G; 2=Other
- treatment is 2 levels e.g. 1=REN001; 2=Placebo
- base12mwd is the Baseline 12MWD

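### The PGIC ANCOVA and PGIC imputation model leave out baseline PGIS for the same symptom, which is already collected and would be a cheap, plausibly useful covariate

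*SAP*

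**What the plan says.** SAP 10.3.8 uses ANCOVA for the two PGIC numeric scores and sets out its terms in one sentence: "The model will include a fixed term for treatment and the mutation stratification factor and continuous baseline distance walked during the 12MWT as covariates". That model is reused for the while-on-treatment supplementary analysis, and the responder logistic regression has the same covariates. The code in SAP Appendix 1 agrees:

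- item 6 (ANCOVA): "model pgic=mutation base12mwd treatment / ddfm=kr solution"
- item 7 (responder logistic): "model pgic=mutation base12mwd treatment/expb"
- item 8 (imputation, run separately by arm): "monotone logistic(pgic=mutation base12mwd / details"

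Imputation applies only if more than 5% of subjects have no PGIC (SAP 10.3.8). Protocol 8.5.2 gives the same covariates for PGIC muscle symptoms.

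PGIS is recorded for both symptoms. SAP 4.6 says: "At Screening, Baseline, Week 4, Week 12, Week 18 and Week 24 visits, the subject will be asked to rate the severity". It is also taken at Early Termination. The PGIS model in SAP 10.3.3 does use its own baseline: "The model will also include the stratification mutation factor, baseline score and baseline distance walked during the 12MWT as covariates". On the status of the PGIC scores, SAP 4.3 says: "These scores are exploratory endpoints".

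**The concern.** PGIC asks once, at the end of treatment, how the severity of a symptom has changed. PGIS rates the severity of that symptom beforehand. Baseline severity is therefore a plausible predictor of reported change, and it is already in the database. Every other patient-reported score that the SAP models (PROMIS, PGIS, SF-36, MFIS, BPI, WPAI) is adjusted for its own baseline as well as for baseline 12MWD. PGIC has no baseline of its own, and the nearest substitute is unused without explanation. By contrast, SAP 10.3.9 does say why the 6-minute distances omit their own baseline.

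Two things are at stake, both small. The ANCOVA may be less precise than it could be. And if imputation is triggered, missing PGIC values would be drawn from genotype and walking distance within arm, with no symptom information. A subject who withdraws after Week 12 without a PGIC may have PGIS at Baseline, Week 4 and Week 12, none of which would be used. Missing at random is easier to defend given the course of the same symptom than given walking distance alone.

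**Working it through.** **The plan's own figure.** The documents give no power, SD or effect size for PGIC. The only sample-size figure is for 12MWD (SAP 3.5): effect 60 m, SD 125 m, two-sided 5%, 90% power.

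- Normal approximation: n per arm = 2 × (1.960 + 1.282)² × 125² / 60² = 91.2, rounded up to 92.
- Exact t-test: power 0.8994 at 92 per arm and 0.9025 at 93 per arm.

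The stated 93 per arm (186 in total) reproduces. It is used here only to set N; about 200 are to be randomized.

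**ANCOVA.** Let r be the partial correlation of PGIC with baseline PGIS, given treatment, mutation and baseline 12MWD. It is assumed throughout. Adding one numeric covariate gives:

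- SE ratio, residual variance only: √(1 − r²)
- SE ratio with an allowance for estimating the extra term: √[(1 − r²)(1 + 1/(N − 6))], with N = 200
- equivalent extra subjects: 1/(1 − r²) − 1
- power, starting from a nominal 80%: Φ[(1.960 + 0.842)/ratio − 1.960], using the second ratio

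| r (assumed) | SE ratio | with allowance | extra subjects | 80% power becomes |
|---|---|---|---|---|
| 0 | 1.000 | 1.003 | 0% | 79.8% |
| 0.1 | 0.995 | 0.998 | 1% | 80.2% |
| 0.2 | 0.980 | 0.982 | 4% | 81.4% |
| 0.3 | 0.954 | 0.956 | 10% | 83.4% |
| 0.4 | 0.917 | 0.919 | 19% | 86.2% |
| 0.5 | 0.866 | 0.868 | 33% | 89.7% |

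Results at N = 186 agree to within 0.001 on the ratio. The break-even point is where (1 − r²)(195/194) = 1, that is r = √(1/195) ≈ 0.07.

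**Responder logistic model.** This was simulated with 100 subjects per arm and 1,500 runs per value of r. The responder indicator was a cut on a latent normal score that depended on treatment, mutation, baseline 12MWD and baseline PGIS. The data model is an assumption.

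| r (assumed) | SE of log OR, without → with PGIS | power, without → with PGIS |
|---|---|---|
| 0 | 0.331 → 0.332 | 67.5% → 66.9% |
| 0.2 | 0.330 → 0.336 | 67.3% → 69.5% |
| 0.3 | 0.331 → 0.343 | 65.1% → 66.8% |
| 0.5 | 0.330 → 0.364 | 65.4% → 72.5% |

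The standard error rises. Any power gain comes from the conditional log odds ratio moving away from zero (at r = 0.5, from 0.78 to 0.93).

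**Imputation.** SAP 8.3.1 builds the primary-endpoint imputation from the mutation factor and the walk distance at every scheduled time point. For PGIC the same section uses only the analysis covariates. So the SAP already uses information from other visits to support missing at random, but not for PGIC.

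**The case against.** The strongest reply is that no defect has been shown. PGIC is exploratory, is outside the fixed sequence in SAP 8.2, and carries no power claim. The covariates are those of the protocol. Leaving an optional prognostic covariate out of a randomized comparison causes neither bias nor type I error inflation. All of that stands, and it limits the point to efficiency.

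The gain is also unknown. PGIC rates change, so its link with starting severity may be weak, and below r of about 0.2 the benefit is under 2% of the SE. That stands too. The comparison with the other models is imperfect, because those outcomes are repeated scores with a baseline of their own.

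A five-level scale might give sparse categories and cost up to four degrees of freedom. A numeric score meets this with one degree of freedom, and SAP 8.3 already lets a screening value replace a missing baseline.

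On imputation, it is fair to say that the need is conditional on the 5% rule and that the latest PGIS would come from different visits in different subjects, which calls for a definition. SAP 8.3.1 does tie the PGIC imputation covariates to the analysis model, but the primary imputation in the same section goes beyond its analysis covariates.

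Three stronger readings are tempting but not supported:

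- **That a subject rated Absent at baseline cannot improve.** PGIS covers the past 7 days and PGIC the time since starting the study, so this is limited room rather than a strict ceiling. Entry requires exercise intolerance or active muscle pain, and the documents give no baseline PGIS distribution.
- **That PGIC is the only direct patient rating of change.** SF-36 has a perceived-change item (SAP 4.8).
- **That all three PGIC models lose precision.** The logistic results show otherwise.

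**Conclusion.** The point holds as a minor efficiency improvement for the ANCOVA and, if it is used, the imputation model. Baseline PGIS for the same symptom is available, plausibly prognostic and unused, with no reason stated. The ANCOVA gain is about 2% to 8% of the SE for an assumed r of 0.2 to 0.4. At r = 0.1 it is between 0.2% (with the allowance) and 0.5% (without), and at r = 0 there is a loss of about 0.3%. The documents do not fix r, so a reader should not conclude that a definite amount of precision is being lost. The argument for the imputation model concerns the credibility of missing at random and does not rest on the baseline correlation. For the responder model, inclusion is a matter of choice: power may rise modestly, and the odds ratio becomes conditional on baseline severity.

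**What to change.** By SAP amendment before database lock, as SAP section 2 requires:

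1. In 10.3.8 and Appendix 1 item 6, add same-symptom baseline PGIS as a numeric score, with the screening value if baseline is missing. Apply this to the main PGIC ANCOVA and the while-on-treatment version.
2. In 8.3.1 and Appendix 1 item 8, add baseline PGIS and the latest available post-baseline PGIS to the PGIC imputation model, for use if the 5% rule is triggered. State how the latest value is chosen and what happens when a subject has none.
3. For the responder logistic model (item 7), either add baseline PGIS and note that the odds ratio is then conditional on it, or leave the model as it is.

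If the sponsor prefers not to change the models, one sentence giving the reason is enough. The cost is a few lines of text and code and one degree of freedom in the ANCOVA. No new data are needed.

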Figure 2: Sources of Energy During Exercise

Adapted from Human Physiology: *An Integrated Approach*, Sixth Edition (2013) Dee Unglaub Silverthorn

Although, the 6MWT is a good measure to assess the submaximal level of functional capacity, the 6MWT duration is not sufficient to fully capture the potential benefits on physical endurance caused by improvements in mitochondrial function. In contrast, the self-paced 12MWT assesses the submaximal level of functional capacity during the period of exercise supported by mitochondrial function. A prior clinical trial conducted by the Sponsor (REN001-101), showed that subjects with PMM progressively slowed their walking speed over the course of the 12MWT, with the greatest decline occurring from minute 6 to minute 9, coinciding with the increased requirement for mitochondrial oxidative phosphorylation [data on file]. Most patients do not achieve maximal exercise capacity during the test; rather, they choose their own intensity of exercise and, if needed, are allowed to stop and rest during the test. This approximates to the activities of daily living, which are typically performed at submaximal levels of exertion for periods of more than 6 minutes.

One limitation of all walk tests is an associated ‘training’ effect whereby subjects may improve the distance walked on subsequent tests due to familiarity with the test (Kierkegaard & Tollback, 2007). This effect can be seen regardless of the interval duration (weeks to months) between tests (Wu et al, 2003; Prahm et al, 2014; Knak et al, 2017; Karaa et al, 2018). Various methods have been used to overcome this effect, such as 1) conducting two walk tests on the same day and using the longest distance (Kierkegaard & Tollback, 2007); 2) correcting the distance walked using average heart rate during the test (Knak et al, 2017); or 3) conducting a walk test at screening to act as a familiarization walk test (Karaa et al, 2018). In this study the training effect will be minimized using a screening, familiarization 12MWT. To minimize variability attributed to the training effect the Screening and Baseline 12MWTs in this study have been set at a minimum of at least 4 weeks apart, subsequent 12MWTs in the study will be 12 weeks apart at Weeks 12 and 24.

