3.2.5. Exploratory Endpoints

- Changes from Baseline at Week 12 and 24 in:
 - number of sit to stands in 30 seconds using the sit to stand (STS) test
 - step count pedometer data
 - Patient Global Impression of Severity (PGIS) score for muscle symptoms and for fatigue symptoms
 - 36 Item Short Form Survey (SF-36) domain scores
 - MFIS Total, Physical, Cognitive and Psychosocial sub-scale scores
 - Brief Pain Inventory (BPI) Short Form pain severity and pain interference scores
 - Work Productivity and Activity Impairment questionnaire: Specific Health Problems (WPAI:SHP) scores
 - First 6-minute walk distance and last 6-minute walk distance*
 - Phenotypic description questions at Week 24 only*
- PGIC score for muscle symptoms and for fatigue symptoms at the end of treatment

- PGIC score for muscle symptoms and for fatigue symptoms responder (‘Very Much Improved’ or ‘Moderately Improved’) at the end of treatment*.

** Note these endpoints were not defined in the protocol.*

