14. CHANGES FROM PLANNED ANALYSES SPECIFIED IN THE PROTOCOL

- The secondary endpoints have been updated following FDA advice. The PROMIS T-score has been promoted to a secondary endpoint and MFIS physical sub-scale score and PGIC (muscle symptoms) have been moved to exploratory endpoints. The order of testing of endpoints has also been updated to align with this change.
- As the PGIC is assessed at the end of study treatment (Week 24 or Early Termination) a while on treatment strategy was proposed in the protocol. However, with some subjects not completing their PGIC assessment until more than a week after their last dose of study medication the strategy has been changed. The primary analysis will include all recorded data, regardless of the duration between the subject's last dose of study medication and the assessment. Given some subjects will have been off treatment for more than 7 days before recording PGIC, this analysis will no longer be referred to as a 'while on treatment' strategy; instead, this is a 'treatment policy' strategy. Subjects with no PGIC assessment will be considered as missing unless the incidence of missing PGIC data exceeds 5%. If the incidence exceeds 5% a multiple imputation approach will be used. A 'while on treatment' strategy has also been included as a supplementary analysis, where only assessments within 7 days of the last dose of study treatment will be included.
- A responder endpoint has been defined for the PGIC muscle symptoms and PGIC fatigue symptoms in addition to the 7-point scale endpoints.
- Two additional exploratory endpoints based on the 12MWD have been defined to further support the primary analysis. The endpoints are the first and last 6-minute periods of the 12MWD and aim to investigate whether there is a difference in treatment effect in these two periods.
- The supplementary analysis for the primary endpoint using a while on treatment strategy has been updated to an ANCOVA following review comments from the FDA. The original while on treatment analysis proposed in the protocol is now referred to as a treatment period restricted analysis.
- Added the exploratory endpoint for the phenotypic description questions (exercise tolerance, gait stability and myopathy) which are asked at Baseline and Week 24.

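### The first-6 and last-6-minute endpoints aim to show whether the treatment effect differs between the two periods, but no estimate with a confidence interval of that difference is planned

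*SAP*

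**What the plan says.** SAP 3.2.5 lists "First 6-minute walk distance and last 6-minute walk distance" among the exploratory endpoints and notes that the protocol did not define them. SAP 14 gives two reasons for adding them: to support the primary analysis, and because they "aim to investigate whether there is a difference in treatment effect in these two periods".

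SAP 10.3.9 sets the analysis: "The first and last 6-minute walk distances derived from the 12MWD will be analysed in the same way as the primary analysis". On the model terms it says: "The model will include fixed terms for treatment, visit and the treatment-by-visit interaction". The covariates are the mutation stratification factor and baseline 12MWD. On the period's own baseline it says: "The baseline 6-minute walk distance will not be included in the model as a covariate".

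The one output specified as showing both periods together is a set of mean plots with 95% confidence intervals, which "will be presented by treatment group and 6-minute time period with visit on the x-axis".

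SAP 4.1 derives the last-6 distance by subtracting the first-6 distance from the total. The first-6 distance counts whole 20 m laps only.

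**The concern.** The quantity named in SAP 14 is the treatment effect in the last six minutes minus the treatment effect in the first six. Nothing in SAP 10.3.9, in SAP 10.4 or in the Appendix 1 code estimates it. There is no period factor, no treatment-by-period interaction and no last-minus-first outcome; the repeated factor in the code is visit. The plots carry intervals for group means, which are not intervals for a difference between two treatment effects.

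The question matters to the trial's reasoning. Protocol 3.3 prefers the 12-minute walk because "the 6MWT duration is not sufficient to fully capture" the potential benefit on endurance, and it reports that the greatest slowing in the pilot study came between minutes 6 and 9. A contrast between periods is a natural, if imperfect, check on that argument. Without a planned estimate, readers are left to set two results from the same walk beside each other. If one is significant and the other is not, that can look like a period effect when there is none.

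**Working it through.** **1. The plan's own figure.** SAP 3.5 gives a difference of 60 m, SD 125 m, two-sided 5% and 90% power, with 93 per arm (186). The normal-approximation formula gives 92 per arm (184). At 93 per arm the power is 90.5%, or 90.3% from the noncentral t. The stated figure reproduces. The documents give no SD, correlation or effect for either half of the walk, so everything below is illustrative.

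**2. Unequal halves.** Assume change SDs of 60 m (first, F) and 75 m (last, L), with their sum T having the plan's SD of 125 m and 93 per arm.

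- Implied correlation: (125² − 60² − 75²) / (2 × 60 × 75) = 6400 / 9000 = 0.711.
- SE factor: √(2/93) = 0.1466.
- SE of each period's effect: 60 × 0.1466 = 8.8 m; 75 × 0.1466 = 11.0 m.
- SE of the difference if treated as independent: √(60² + 75²) × 0.1466 = 14.1 m.
- SE of the difference within subject: √(60² + 75² − 6400) × 0.1466 = √2825 × 0.1466 = 7.8 m.
- A difference in effects of 20 m would be z = 20/14.1 = 1.4 on the first basis and 20/7.8 = 2.6 on the second.

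**3. Equal halves over a range of correlations r.** Here each half has SD 125/√(2(1+r)), and SD(L − F) = 125 × √((1−r)/(1+r)). The power column assumes that the 60 m effect splits 20 m and 40 m. The last column is a simulation in which both halves truly gain 30 m.

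| r | SE within subject (m) | 95% CI half-width (m) | SE if independent (m) | Power for a 20 m difference | Exactly one half significant, equal effects |
|---|---|---|---|---|---|
| 0.5 | 10.6 | 20.7 | 15.0 | 47% | 22% |
| 0.7 | 7.7 | 15.1 | 14.1 | 74% | 14% |
| 0.8 | 6.1 | 12.0 | 13.7 | 90% | 10% |
| 0.9 | 4.2 | 8.2 | 13.3 | 99.7% | 7% |

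The within-subject SE is smaller in every row. The last column shows how often two separate significance statements would suggest a period difference that does not exist.

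**4. Lap rounding.** The unrecorded part-lap at minute 6 is taken as uniform on 0 to 20 m, SD 20/√12 = 5.8 m. It leaves the first half and enters the last, so it counts twice in L − F: 11.5 m. Over two visits, 11.5 × √2 ≈ 16 m. Added to the SD in step 2, √(2825 + 16²) = 55.5 m, and the SE rises from 7.8 to 8.1 m.

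**5. Imputed values and a signed difference.** SAP 8.3.1 sets the distance to 0 m for death and for a non-ambulatory subject. Both halves are then 0, so L − F = 0. A subject who slows during the walk has a baseline difference of −d, with d > 0. The change is 0 − (−d) = +d, so death or loss of ambulation would score as an improvement. The worst-case draws raise a similar problem: under SAP 10.3.9 they can apply to the last half alone, no joint draw for the two halves is specified, and the floor of 0 m has no meaning for a quantity that can be negative.

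**The case against.** The strongest reply is that little hangs on this. The endpoints are exploratory and lie outside the two-step testing sequence in SAP 8.2. SAP 14 speaks of investigating a difference, not testing one. All of that stands.

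A reader might infer that the trial could not answer the question at all. The documents do not support that. Both period models use the same covariates, and for observed walks first plus last equals total, so subtracting the two planned estimates gives the point difference. For complete data its SE is roughly recoverable from three planned analyses: Var(L − F) = 2Var(F) + 2Var(L) − Var(T). With the SEs in step 2, and 125 × 0.1466 = 18.3 m for the total, this returns 7.8 m. It is only approximate, and imputing the last period alone can break the identity, but the gap is an unplanned contrast, not an unanswerable question.

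A reader might also infer that the SAP intends to compare p-values or to treat the two estimates as independent. No section says so. The 14.1 m figure shows the cost of an informal reading, not of a planned method.

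A third tempting step is to fault the period models for leaving out their own baseline: "The baseline 6-minute walk distance will not be included in the model as a covariate as this will be correlated with the baseline 12MWD". Correlation between covariates is a weak reason, and the PROMIS, 30STS, SF-36 and MFIS models include both the outcome's own baseline and baseline 12MWD. Under randomisation, though, the omission can cost precision, not validity. Keeping the same covariates in both models also keeps the two estimates close to additive. There is no good case for changing this.

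Finally, six minutes is not a clean biological boundary. Protocol 3.3 places the switch to oxidative phosphorylation at about four minutes, so the first half already contains some of the period of interest. The contrast would support the protocol's rationale but would not prove it.

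**Conclusion.** The point holds in a limited form. SAP 14 names a difference in treatment effect between the two periods as an aim, and the planned analyses give no estimate of it with a confidence interval. The primary inference, the type I error and the sample size are unaffected.

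On assumed half-walk SDs of 60 and 75 m, the within-subject SE is 7.8 m against 14.1 m if the correlation is ignored. With equal SDs and correlations of 0.5 to 0.9, it is 10.6 to 4.2 m against 15.0 to 13.3 m. The exact sizes rest on SDs, correlations and effect splits that the documents do not give. That the within-subject SE is the smaller needs only a positive correlation between the two halves. This is a cheap improvement, not a defect in the trial's main analysis.

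**What to change.** In SAP 10.3.9, add one exploratory model outside the testing sequence.

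- Outcome: the within-subject change from baseline in last-6 minus first-6 distance.
- Model: the same MMRM, with mutation factor, baseline 12MWD and the baseline of that difference as covariates.
- Report: the Week 24 treatment contrast with its 95% CI, as the difference in effect between periods.
- Data: walks with both halves observed, with missing values handled as missing at random. Do not apply the 0 m or worst-case values to the signed difference.
- Sensitivity: form the difference from the two halves within each imputed dataset, with a note that subjects set to 0 m in both halves can appear to improve.
- Leave the covariates of the two period models as planned.

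The cost is one more exploratory table. Lap rounding adds about 16 m SD to the change in the difference. The main contrast describes walks with both halves observed, so it does not follow the treatment-policy estimand, and the report should say so.
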